10.3.1.2 Visual Index for Ichthyosis Severity – Scaling

The secondary endpoint is the number of subjects in each treatment group who experience a severity score of 0 or 1 at Week 12/EOT on the overall 16-point VIIS for scaling.

The investigator will rate the subject's condition using the 5-point VIIS for each body area (chest/abdomen, back, legs, and arms) and an overall score at each time point shown in the Schedule of Events (Section 2.2):

0	Normal skin; no perceptible scale or smoothening
1	Areas of normal skin intermixed with areas showing smoothening (diminished fine skin markings, shininess, waxiness) or small scales (visibly separated/fractured stratum corneum)
2	Confluent smoothening (diminished fine skin markings, shininess, waxiness) or small scales (visibly separated/fractured stratum corneum)
3	Confluent scales (visibly separated/fractured stratum corneum) including some large (>1 cm), thick scales
4	Confluent, primarily large, thick scales

10.3.1.3 Individual Score for Roughness

The amount of roughness of the skin overall will be measured on a 5-point scale.

0	Clear	Smooth skin
1	Almost Clear	Hardly palpable roughness
2	Mild	Mild roughness (fine sand paper-like)
3	Moderate	Moderate, coarse roughness (coarse sand paper-like)

- | | | |
|---|--------|---|
| 4 | Severe | Very coarse skin (broken cornflakes-like) |
|---|--------|---|

10.3.1.4 Palm/Sole Assessment

Thickening of the skin on the palms and soles will be measured on a 5-point scale.

- | | | |
|---|--------------|---|
| 0 | Clear | No thickening, no roughness, no fissure |
| 1 | Almost Clear | Only slight thickening, minimal to no roughness, no fissures |
| 2 | Mild | Some thickening, mild roughness on palpation, few fissures may be present |
| 3 | Moderate | Substantial and diffuse thickening, coarse roughness on palpation may be present, fissures may be present |
| 4 | Severe | Very thickened and rough skin, numerous fissures |

10.3.1.5 Palm/Sole Fissuring Assessment

Fissuring will be assessed by recording the presence or absence of fissures, the number of fissures present, and the pain associated with each fissure. A fissure is a longitudinal and deep crack that separates the stratum corneum and may penetrate down to the dermis, causing pain and sometimes bleeding. The subject will assess pain associated with fissures as ranging from 0-3 (none, mild, moderate, severe).

10.3.1.6 Dermatology Life Quality Index

The DLQI is a dermatology-specific Quality of Life instrument. It is a simple 10-question validated questionnaire with 6 domains (symptoms and feelings, daily activities, leisure, work and school, personal relationships, and treatment); higher scores indicate poorer quality of life. The DLQI is the most frequently used instrument in studies of randomized controlled trials in dermatology.

10.3.1.7 EQ-5D Quality of Life Questionnaire

The EQ-5D is a standardized instrument developed by the EuroQol Group as a measure of health-related quality of life used in a wide range of health conditions and treatments. The EQ-5D consists of a descriptive system and the EQ visual analog scale (VAS).

The descriptive system comprises 5 dimensions: mobility, self-care, usual activities, pain/discomfort, and anxiety/depression. The EQ VAS records the subject's self-rated health on a vertical 0-100 VAS. This can be used as a quantitative measure of health outcome that reflects the subject's own judgment.

10.3.1.8 Ectropion Severity Score

The Ectropion Severity Score (ESS), has a maximum score of 8 points. A higher score indicates a worse ectropion. The score takes the severity of ectropion in terms of lateral and medial apposition, scleral show, conjunctival show, and roundness of the eye into account and gives an indication of

the functional aspects involved in ectropion by scoring redness, excess tear film, and the position of the lacrimal punctum.¹⁴

	Points per Item		
	0	0.5	1
Lateral apposition	Nonaffected	—	Affected
Medial apposition	Nonaffected	—	Affected
Sceral show	No	≤1 mm	>1 mm
Conjunctival show	No	—	Yes
Excess tear film	No	—	Yes
Redness of the eye	No	—	Yes
Round canthus	No	—	Yes
Punctum lacrimale	Invisible	Emerging	Visible
Maximum score			8 points

Figure 10-1: Ectropion Severity Score

Source: Korteweg SFS, Stenekes MW, van Zyl FE, Werker PMN. Paralytic Ectropion treatment with lateral periosteal flap canthoplasty and introduction of the ectropion severity score. *Plast Reconstr Surg Glob Open*. 2014;2(5):e151.

10.3.1.9 Photography Substudy

All sites that have photographic capability will take photographs as source data to support scoring at Baseline, Day 30, and Day 90. A central reader who will not be an investigator in the study will review the photographs to assess consistency of investigator scoring of LI severity as a quality check. Photographs may also be used for scientific publication purposes. Subjects will sign a separate, optional photographic informed consent form (ICF).

10.3.2 Clinical Pharmacology

10.3.2.1 Pharmacokinetic Analysis Methods

The pharmacokinetic characterization of drug concentrations for each dose to be profiled will use noncompartmental analysis (NCA).

10.3.2.2 Pharmacokinetic Parameters

Samples for PK will be drawn from all subjects at Baseline and at each clinic visit for trough values.

Subjects who provide written informed consent to participate in the optional PK substudy will provide blood samples for PK analysis predose on Day 1 and at 1, 2, 4, 8, 12, and 24 hours postdose on Day 1 and Day 30.

The PK parameter estimates will be completed using WinNonlin (Pharsight Corporation) software using the actual elapsed times from dose administration to sample collection (i.e., not nominal time).

Standard PK parameters assessed will include measures of the extent of absorption using estimates of the area-under-the-curve (AUC) and rate-of-absorption using the maximum concentration (C_{max}) and the time of C_{max} (T_{max}). Additional details of the parameters and their calculation and evaluation will be included in the statistical analysis plan (SAP).

Table 10-1 shows the PK parameters that will be computed for each subject for samples obtained over the planned sampling intervals.

Table 10-1: Pharmacokinetic Parameters

Parameter	Description of Parameter
C_{max}	Maximum (or peak) serum concentration
T_{max}	Time at which C_{max} is observed
$AUC_{(0-t)}$	Area under the plasma concentration-time curve from time 0 to the time of the last quantifiable plasma concentration
$AUC_{(0-inf)}$	Area under the plasma concentration-time curve from time 0 to infinity (if data permit)
$t_{1/2}$	Apparent first order terminal elimination half-life
λ_z	Apparent terminal phase rate constant (if data permit)

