At all sites with photographic capability, photographs will be taken as source data to support scoring at Baseline, Day 30, and Day 90. A central reader who will not be an investigator in the study will review the photographs to assess consistency of investigator scoring of LI severity as a quality check. Photographs may also be used for scientific publication purposes. Subjects will sign a separate, optional, photographic informed consent form (ICF).

Samples for PK will be drawn from all subjects at Baseline and at each clinic visit, as indicated in the Schedule of Events (Table 2-1). Visits for PK must occur at least 24 hours after the last application of the IP to avoid contamination of the blood samples with any IP that may have remained in the skin after the last application. Subjects should not apply IP on visit days until after the visit.

In addition, a PK substudy will be conducted on Days 1 and 30 at sites with the capability to conduct it. Participation in the PK substudy will be optional and will include at least 30 subjects. Subjects who participate in the PK substudy will come from both study cohorts and will undergo serial blood sampling predose and at 1, 2, 4, 8, 12, and 24 hours postdose on Day 1 and Day 30. Trough levels will be drawn for all subjects at specified time points. For the subjects in the PK substudy, postdose ECGs will be performed at each serial blood draw on Day 1 and Day 30.

Efficacy will be assessed by the number of subjects in each treatment group who achieve “success” defined as clear/almost clear overall and at least a 50% reduction from Baseline at Week 12/end-of-treatment (EOT) in the Double-blind Period on the 5-point IGA scale (i.e., 0 = clear; 1 = almost clear; 2 = mild; 3 = moderate; 4 = severe). In addition, efficacy criteria include assessment scales for palm/sole, scaling, roughness, fissuring, and the Dermatology Life Quality Index (DLQI), and the EQ-5D Quality of Life (QoL) Questionnaire. Ectropion Severity Scores (ESS) between the active trifarotene cream HE1 and vehicle groups will be an exploratory endpoint.

Plasma concentrations of CD5789 and its major metabolites will be measured.

Safety will be assessed by evaluating reported adverse events (AEs), changes in clinical laboratory test results, vital sign measurements, physical examinations, 12-lead ECGs, and local tolerability.

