9.2. Treatments Administered

For the Double-blind Treatment Period, a fixed dose (determined at Visit 2) of trifarotene cream HE1 100 µg/g or 200 µg/g or vehicle cream will be applied topically twice weekly on up to 90% BSA of each subject. The IP should be applied thinly and gently rubbed in.

Study staff will apply the first administration of IP in the clinic on Day 1 after Baseline measurements, and the amount of IP used will be measured (i.e., 50-g tube will be measured before and after application to determine amount used). If the product will be applied at home by someone other than the study subject, it is recommended that this person assist with application at the first visit to learn how the IP is applied.

The maximum dose per application is 36 g (i.e., 1 tube). Subjects will receive an adequate number of tubes to use 1 tube per application and will use a new tube for each treatment day. Subjects may use less than full amount of product in a tube. Subjects will continue treatment for up to 12 weeks.

After the Day 1 visit, subjects will apply approximately the same amount (up to 36 g) of study drug as for the first dose on up to 90% of BSA twice weekly, sparing the scalp, inguinal, and axillary areas. Subjects with heavy facial hair should not apply IP to hair-bearing areas. Persons other than the study subject applying the study drug must wash their hands after application or use disposable vinyl gloves. In addition, a long-handled applicator will be provided for application on the back. The applicator must be washed with warm water and soap after every application.

Trifarotene cream should not come into contact with the eyes, mouth, angles of the nose, or mucous membranes. For the ectropion treatment, Q-tips are recommended for precise application on eyelids, without contact to the eye or conjunctiva. If the IP gets into the eye, it must be flushed immediately with warm water. In case of eye irritation, the subject must be seen by an ophthalmologist.

For the OLE, all subjects will receive trifarotene cream HE1 200 µg/g and apply the same fixed dose in the same manner as in the Double-blind Period for an additional 12 weeks.

Visits for PK must occur at least 24 hours after the last application of the IP to avoid contamination of the blood samples with any IP that may have remained in the skin after the last application.

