Subjects should not apply IP on visit days until after the visit, unless they are participating in the PK substudy, in which case the IP will be applied in the clinic on Day 30 after the blood draw. Among subjects participating in the PK substudy, ensure the PK line is inserted before study drug application to prevent contamination with the IP and to protect the skin around the needle insertion point from study drug application.

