9.3. Selection of Timing of Dose for Each Subject

Subjects will be randomized in a 1:1:1 ratio to trifarotene cream HE1 100 µg/g or 200 µg/g or vehicle cream. After Day 1, on which the study staff will apply the first administration of IP in the clinic, each subject will apply approximately the same amount of IP on up to 90% of their BSA twice weekly. It is suggested that each subject choose 2 specific days per week at least 3 days apart on which to apply their IP (e.g., Tuesday and Friday), and maintain that regimen throughout the study. Visits for PK must occur at least 24 hours after the last application of the IP to avoid contamination of the blood samples with any IP that may have remained on the skin after the last application. Subjects should not apply the IP on visit days until after the visit, unless they participate in the PK substudy, in which case the IP will be applied in the clinic on Day 30 after the PK blood draw.

All subjects will be provided with diaries in which to record study drug application (days/times) and any areas of skin not treated (e.g., due to local reactions).

If a subject misses an IP application, they should apply the IP as soon as they remember and record the date/time in the subject diary, then wait at least 3 days and continue their regimen.

Subjects should not shower, bathe, or swim for at least 4 hours after IP application. No occlusive dressings should be used on areas to which IP is applied.

Subjects who continue into the Open-label Extension will receive trifarotene cream HE1 200 µg/g and apply the same fixed dose in the same manner as in the Double-blind Period for an additional 12 weeks.

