10.3.3 Sample Collection

Samples will be collected at the time points specified in the Schedule of Events (Section 2.2). Specimen preparation, handling, shipment, and storage for the complete blood count, chemistry, and urinalysis are described in the study laboratory manual. Finding veins in subjects with this disease can be challenging. Blood draws will be done at the corresponding study visits before application of the IP and should be 24 hours after IP application. Subjects must not apply the IP to the area where blood will be drawn within 24 hours before their next study visit to avoid contamination of the blood by IP that remained in the skin. For subjects in the PK substudy, a cannula should be placed before IP application and the cannula site may be occluded to prevent contamination with IP.

Actual PK sample times for subjects in the PK substudy will be recorded in the eCRF.

Blood

For subjects not in PK substudy:

The expected amount of blood to be drawn at each visit varies from approximately 6 mL to a maximum of 21 mL (Screening Visit only). The total amount of blood drawn for the study will be about 123 mL per subject, unless the subject takes part in the PK substudy.

For subjects in PK substudy:

For subjects who opt to participate in the PK substudy, extra blood samples will be drawn at Visit 2 and at Visit 4 for PK analysis. The amount of blood to be drawn per subject at each of these visits

will be approximately 54 mL. For subjects taking part in the substudy, the total amount of blood drawn for the entire study will be approximately 195 mL.

Urine

Urinalysis will be performed at central laboratory. Dipstick and urine pregnancy tests will be conducted on site.

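### PK samples called troughs for all subjects are not tied to the end of the dosing interval, and actual draw times are required only in the substudy

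*Protocol*

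**What the plan says.** The protocol calls the visit samples troughs in two places. Section 10.3.2.2 states: "Samples for PK will be drawn from all subjects at Baseline and at each clinic visit for trough values". Section 7.1 states: "Trough levels will be drawn for all subjects at specified time points".

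The dosing interval follows from Section 9.3, which suggests that "each subject choose 2 specific days per week at least 3 days apart on which to apply their IP", with Tuesday and Friday as the example.

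The timing of the draw is governed by these statements:

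- Section 9.2: "Visits for PK must occur at least 24 hours after the last application of the IP to avoid contamination of the blood samples". Sections 7.1 and 9.3 and the notes to Tables 2-1 and 2-2 give the same minimum.
- Section 10.3.3: "Blood draws will be done at the corresponding study visits before application of the IP and should be 24 hours after IP application". This reads as a point, not a minimum.
- Section 9.2: "Subjects should not apply IP on visit days until after the visit", with an exception for the Day 30 substudy visit.

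On recording, Section 10.3.3 says: "Actual PK sample times for subjects in the PK substudy will be recorded in the eCRF". It says nothing about draw times for other subjects. Sections 9.3 and 9.5 have every subject record application days and times in a diary, and diary information is transcribed to the eCRF for compliance. Section 13.1.5.1 lists concentrations and summarises them descriptively at each time point.

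**The concern.** A trough is the concentration at the end of a dosing interval. Here the label is attached to samples whose only timing rule protects against contamination of the blood draw. A site that takes Section 10.3.3 literally draws at 24 h, which is the last point of the substudy profile. A site that follows Section 9.2 or 9.3 may draw at 24, 48, 72 or 96 h. All of these draws comply, and all would be reported as troughs.

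Systemic exposure under twice-weekly use is a secondary objective (Section 6.2). The substudy is optional and planned for at least 30 of about 120 subjects, so for up to about 120 − 30 = 90 subjects the visit samples are the only exposure data. They are also the only PK data in the open-label extension (Weeks 16 and 24). If elapsed time drifts from visit to visit, a summary by visit can suggest or hide accumulation.

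**Working it through.** The protocol gives no sample size, power or expected concentration for these samples, so there is no planned figure to reproduce.

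**Step 1: the permitted window.** Two fixed days per 7-day week, at least 3 days apart, force gaps of 3 and 4 days, that is 72 h and 96 h. The earliest compliant draw, at 24 h, lies at 24/96 = 25% to 24/72 = 33% of the interval. No upper limit is set. A missed application, or a tolerability reduction under Section 9.4, can lengthen the gap further.

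**Step 2: how far a 24 h value can lie from a trough.** The documents give no half-life T, so it is an assumption. With mono-exponential decline, C(24)/C(τ) = 2^((τ − 24)/T).

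| Assumed T | 24 h vs 72 h: 2^(48/T) | 24 h vs 96 h: 2^(72/T) |
|---|---|---|
| 12 h | 16 | 64 |
| 24 h | 4 | 8 |
| 48 h | 2 | 2.8 |
| 72 h | 1.6 | 2.0 |

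**Step 3: what this does to a comparison between arms.** Suppose draws are spread uniformly over 24–96 h, identically in each arm, and elapsed time is ignored. The log-scale SD from timing alone is (ln 2/T) × 72/√12, which is 1.20, 0.60, 0.30 and 0.20 for T = 12, 24, 48 and 72 h. Between-subject variation has log SD √ln(1 + CV²), and the two combine as the root of the sum of squares. The calculation takes 32 per arm (the evaluable number in Section 13.2), a two-sided 5% level and an assumed twofold concentration difference.

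| Assumed CV | No timing spread | T = 12 h | 24 h | 48 h | 72 h |
|---|---|---|---|---|---|
| 50% | 1.00 | 0.58 | 0.95 | 1.00 | 1.00 |
| 100% | 0.92 | 0.48 | 0.77 | 0.88 | 0.90 |

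Power falls markedly only for short half-lives.

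**Step 4: what can be recovered without a recorded draw time.** The visit date set against the diary separates draws at about 24, 48, 72 and 96 h. If the clock time within the clinic day is uncertain by ±5 h (an assumption), the remaining error factor is 2^(5/T): about 1.33, 1.16 and 1.07 for T = 12, 24 and 48 h.

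**The case against.** The strongest reply is that this is a labelling slip in a descriptive secondary objective. Several parts of it stand.

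- **Dose comparison.** A reader might infer that the samples cannot show a difference between the two strengths. The documents do not support that. Arms are randomised and blinded on one visit schedule, so mixed timing mainly adds variance, as Step 3 shows. Unequal tapering for local reactions could unbalance it, but that is a possibility and not a stated fact. No dose contrast on these samples is a named objective, and the substudy gives timed profiles by dose.
- **Reconstruction.** A reader might also infer that elapsed time is lost outside the substudy. It is not: visit date and diary give it approximately. The protocol is silent on draw times for these subjects and does not exclude recording them.
- **Benchmark.** The factor of 2 between arms is cream strength. Sections 5.2 and 7.2 report low and comparable plasma levels at both strengths in healthy volunteers, although Section 5.2 cautions that absorption may be greater in lamellar ichthyosis. An expected twofold plasma difference is not established.
- **Loose wording.** The 24-hour point in Section 10.3.3 may be meant as a minimum, since the next sentence there gives contamination as the purpose.
- **Version.** Sections 10.3.2.2 and 10.3.3 are Amendment 2 text. The document also holds statistics sections and a COVID-19 appendix from another, apparently later, version whose Section 10 is not shown, so whether this wording persists cannot be checked.

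None of this rescues the trough label. Even read as a minimum throughout, the rule allows a draw at a quarter to a third of the interval. Nor can an analysis plan supply an exact draw time that was not collected.

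**Conclusion.** In the Amendment 2 text, the all-subject PK samples are not ensured to be troughs. Compliant draws range from 24 h to about 96 h after application, and the two forms of the 24-hour rule need to be reconciled. Exact draw times are required only for substudy subjects; for the rest, elapsed time is approximate.

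The consequence is added variance and possible distortion in descriptive summaries of exposure and accumulation, most of all in the open-label extension, where no other PK data exist. A comparison between arms is weakened, not ruled out. The size rests on an assumed half-life and mono-exponential decline: a 24 h value is about 1.6 times a 72 h value at 72 h, and up to 64 times a 96 h value at 12 h. The power figures further assume uniform timing, elapsed time left out of the analysis, CVs of 50% or 100%, and a twofold plasma difference that the documents do not establish. They illustrate the effect and do not predict it. The change is worth making because it must be made at data collection and is cheap.

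**What to change.** 1. Reconcile the timing wording of Sections 7.1, 9.2 and 9.3 with that of Section 10.3.3.
2. Book each post-baseline PK visit on one of the subject's planned application days, with the sample drawn before that day's application. The ±5-day and ±7-day windows span 11 and 15 days, so each always contains such a day. The existing rule of no application until after the visit already supports a pre-dose draw. If the previous application was on schedule, the draw falls at 72 or 96 h, beyond the contamination minimum.
3. Record draw date and time, and last-application date and time, in the eCRF for all subjects.
4. Label as trough only samples taken in that pre-dose window, and list the others by time since application.

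The cost is protocol wording, two eCRF fields and slightly less freedom in booking visits. Dose, application frequency and number of samples do not change.

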10.3.3 Sample Collection

Samples will be collected at the time points specified in the Schedule of Events (Section 2.2). Specimen preparation, handling, shipment, and storage for the complete blood count, chemistry, and urinalysis are described in the study laboratory manual. Finding veins in subjects with this disease can be challenging. Blood draws will be done at the corresponding study visits before application of the IP and should be 24 hours after IP application. Subjects must not apply the IP to the area where blood will be drawn within 24 hours before their next study visit to avoid contamination of the blood by IP that remained in the skin. For subjects in the PK substudy, a cannula should be placed before IP application and the cannula site may be occluded to prevent contamination with IP.

Actual PK sample times for subjects in the PK substudy will be recorded in the eCRF.

Blood

For subjects not in PK substudy:

The expected amount of blood to be drawn at each visit varies from approximately 6 mL to a maximum of 21 mL (Screening Visit only). The total amount of blood drawn for the study will be about 123 mL per subject, unless the subject takes part in the PK substudy.

For subjects in PK substudy:

For subjects who opt to participate in the PK substudy, extra blood samples will be drawn at Visit 2 and at Visit 4 for PK analysis. The amount of blood to be drawn per subject at each of these visits

will be approximately 54 mL. For subjects taking part in the substudy, the total amount of blood drawn for the entire study will be approximately 195 mL.

Urine

Urinalysis will be performed at central laboratory. Dipstick and urine pregnancy tests will be conducted on site.

